End of Trial Scan: After the 6-week period, subjects will be scheduled to undergo their end of Trial A ¹H-MRS and fMRI scan session, which will take approximately 75 minutes. Subjects will be instructed to present to the Penn Center for Women's Behavioral Wellness approximately 2.5 hours before their scheduled scan to complete cognitive testing and behavioral assessments

regarding their mood and emotions. Subjects will then be escorted to the CMROI by the study CRC where they will be scanned and asked to perform a series of tasks assessing their memory and attention. In total, the end of Trial A scan will require approximately 4 hours to complete. The completion of this visit concludes all visits for Trial A. Upon completion of the visit and Trial A, subjects will be given the study drug for the entirety of Trial B (either placebo or LDX) and instructed to begin taking the medication after the washout period, as directed by the study provider.

Following an approximate 2-week washout period, subjects will complete their Trial B Baseline Visit, initiating the start of Trial B and medication usage. With the exception of the first baseline scan and cognitive testing, subjects will undergo the same study procedures for Trial B as they did for Trial A. Subsequent to their last scan, subjects will be required to bring their scales, blood pressure cuffs and unused capsules/empty bottles back to the study team so that they can be returned to Penn Investigational Drug Service (IDS).

The primary investigator and research staff will unblind themselves to the drug treatment that was administered in each trial upon each participant's completion or discharge from the study.

Remote End of Trial Visit: After the 6-week period, subjects will be scheduled to undergo their end of trial visit which will require approximately two hours. On the day of the remote end of trial visit, subjects will meet remotely with a member of the study team to complete behavioral assessments regarding their mood and emotions and complete cognitive testing. The completion of this visit concludes all visits for Trial A. Upon completion of the visit and Trial A, subjects will return the prescription bottle and any remaining study drug from Trial A so that they can be returned to Penn Investigational Drug Service (IDS). At this point, all subjects will be instructed to complete an approximate 2-week wash out period before continuing to Trial B.

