2.5 Compensation

Participants will be compensated for their participation in all study visits. If the participant completes all parts of the study, is on time for appointments, and takes her medication, total payment for participants is \$650.

The breakdown of subject payment by visit is as follows:

Visit Name	Visit Number	Amount
Screening Visit*	Visit 1	\$50
Trial A		
Baseline (with Scan)	Visit 2	\$150
Week 3*	Visit 3	\$50
End of Trial A (with Scan)	Visit 4	\$150
Trial B		
Baseline (without Scan)*	Visit 5	\$50
Week 3*	Visit 6	\$50
End of Trial B (with Scan)	Visit 7	\$150

Note: “” indicates that study visit can be complete remotely.*

Subject reimbursement is available for:

- Transportation to and from required in-office visits (Visits 2, 4, and 7).

- Hotel accommodations provided by the research team for up to two nights for required in-office visits (Visits 2, 4, and 7)
- Study-related procedures completed with the subject's physician that were NOT covered by the subject's insurance (i.e., EKG, blood work, and physical exam).

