4.1 Statistical Analysis

Summaries of each outcome (BADDs scores, performance on the cognitive tasks, Glut, and BOLD signal) under each treatment condition (baseline, LDX, and placebo) will be examined using histograms, boxplots, and normal probability plots. Transformations of the outcomes will be considered as necessary to meet modeling assumptions. General linear regression (mixed models) will be employed to estimate the association between each outcome, treatment condition and cross-over sequence while accounting for the nonzero correlation among the repeated observations within individuals.

Aim 1: Total BADDs score at each time point will be examined for an interaction effect between time (pre vs. post) and treatment (LDX vs. placebo) to assess whether within-subject total BADDs score is significantly reduced post LDX treatment rather than post placebo. Baseline BADDs scores will be dichotomized at the median score and considered as a covariate in the mixed effects models. Additional interaction terms for baseline group by time (pre vs. post) and baseline group by treatment (LDX vs. placebo) will be added to the model to test whether treatment effects differentially affect those with higher baseline scores.

Aim 2: Similar models will evaluate BADDs subscores, cognitive task performance, and L-DLPFC Glut levels. Similar mixed models will assess associations between change in specific BADDs domains with identified deficits in executive function and change in DLPFC Glut levels.

Aim 3: We will quantify associations between baseline percentage BOLD signal change during performance of the n-back (3-back) and L-DLPFC Glut.

Current methods for fMRI analyses are as follows: Functional scans will be realigned, normalized, time-corrected, and spatially smoothed by an 8 mm FWHW Gaussian kernel. The time series will be high-pass filtered to correct for drift across the scan. For blocked designed experiments (3-back), regressors will represent trial conditions; for the event-related design

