4.2 Rationale for sample size

Sample size is estimated for the 3 primary outcome measures: BADDS scores, DLPFC Glut levels, BOLD signal activation during the N-Back Task.

Assuming a type I, alpha, error of 5%, and 80% power, we anticipate being able to detect a 0.3 SD difference between within subject change under active LDX and placebo conditions with 88 participants. Based on our pilot data for total BADDS score, we will have 80% power to detect as small as an 8.4% difference in BADDS total score when comparing placebo to LDX administration. Given our pilot data from naturally menopausal women, this effect size corresponds to a 19% difference between active LSX and placebo in organization and activation for work, and 15% for attention/concentration BADDS subscales. We are conservatively powered for an effect size of 0.3 SD, meaning that we have sufficient power to examine a number of different covariates and possible predictors of outcome in this study.

Given our pilot data for levels of Glut in the left DLPFC, we will have 80% power to detect as small as a 2.6% reduction in Glut for active LDX administration compared to placebo. A similar 0.3 SD can be detected for BOLD signal in left DLPFC. This corresponds to a 25% difference in BOLD signal change between placebo and LDX for 3-back task.

5 Safety and Adverse Events

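### Aim 2 carries a pre/post-by-treatment interaction over to Glut, which has no Trial B baseline scan; it should name the end-of-trial LDX versus placebo contrast instead

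*Combined protocol and SAP*

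**What the plan says.** **Schedule.** In section 2.1 (End of Trial Scan), the in-office Trial B repeats Trial A with two omissions: "With the exception of the first baseline scan and cognitive testing, subjects will undergo the same study procedures for Trial B". The payment table in section 2.5 agrees. It lists Visit 5 as "Baseline (without Scan") and attaches scans only to Visits 2, 4 and 7. Remote women are tested cognitively at baseline and repeat the Trial A procedures in Trial B, so they have a Trial B cognitive baseline.

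**Analysis.** Under Aim 1 in section 4.1, total BADDs "will be examined for an interaction effect between time (pre vs. post) and treatment (LDX vs. placebo"). Aim 2 then says: "Similar models will evaluate BADDs subscores, cognitive task performance, and L-DLPFC Glut levels". It gives no coding for the baseline and names no contrast. The opening paragraph of 4.1 is more general. It summarises outcomes "under each treatment condition (baseline, LDX, and placebo") and uses mixed models to "estimate the association between each outcome, treatment condition and cross-over sequence".

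**Sample size.** Section 4.2 begins: "Sample size is estimated for the 3 primary outcome measures: BADDS scores, DLPFC Glut levels", with BOLD signal as the third. It continues: "we anticipate being able to detect a 0.3 SD difference between within subject change under active LDX and placebo conditions with 88 participants". For Glut it claims 80% power for a 2.6% reduction on LDX relative to placebo. Sections 1.2 and 1.3 differ from this: they make total BADDs primary and Glut secondary.

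**The concern.** A time-by-treatment interaction compares the pre-to-post change on LDX with the pre-to-post change on placebo. BADDs can supply both changes, because nothing in the schedule removes the behavioural ratings from the Trial B baseline visit. Glut cannot, because it has no scan at the start of Trial B. An analyst who follows Aim 2 literally must either assign the one baseline to Trial A or use it twice.

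The choice decides whether the Glut test uses the within-woman LDX–placebo comparison that the crossover was designed to give, and whether the 80% power in 4.2 applies to the test performed. If it is left open, it could also be settled after the data have been seen.

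**Working it through.** **Inputs.** From 4.2: alpha 5%, power 80%, 0.3 SD, 88 women, Glut 2.6%. From 2.1 and 2.5: three scans. From 4.1: sequence in the model. Assumptions: two-sided test, 44 women per sequence (no ratio is stated), equal variance s² and equal correlation r between scans, and Glut data on all 88.

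**1. The plan's own figure.** n = ((1.960 + 0.842)/0.3)² = 87.2, rounded up to 88. Power at 88 is Φ(0.3√88 − 1.96) = Φ(0.854) = 80%. The stated figure is reproduced as a paired comparison, with 0.3 in units of the SD of a within-woman difference.

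**2. Baseline coded to Trial A, sequence in the model.** Let b, A and B be the mean Glut at baseline, end of Trial A and end of Trial B. Subscript 1 is LDX first and 2 is placebo first.

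- Sequence effect, from the post scans (each sequence has one LDX and one placebo scan): ½(A₁ + B₁) − ½(A₂ + B₂).
- Post difference, LDX minus placebo: ½(A₁ − B₁) + ½(B₂ − A₂).
- Pre difference, after removing sequence: (b₁ − b₂) − ½(A₁ + B₁) + ½(A₂ + B₂).
- Interaction = post difference − pre difference = (A₁ − b₁) − (A₂ − b₂).

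B₁ and B₂ cancel, leaving a parallel-group comparison of Trial A change. The only information left over is the overall end-A versus end-B difference, which is a period effect. A period term uses it up, so the zero weight is then exact at any allocation. Without a period term it is exact at 44:44. At 46:42, 50:38 and 58:30 the end-B weight is −0.02, −0.07 and −0.16. It is the same in both sequences, so it carries no LDX–placebo information.

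**3. Variances at 44:44**, in units of s²(1 − r)/88.

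- Interaction above: two independent mean changes, each 2s²(1 − r)/44, which sum to **8**.
- End-of-trial contrast, ½(A₁ − B₁) − ½(A₂ − B₂): ¼ × 2 × 2s²(1 − r)/44, which is **2**.
- Ratio: 8/2 = **4**, whatever r is.

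**4. Consequence if 0.3 SD refers to the end-of-trial difference.**

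- Power: Φ(0.3√(88/4) − 1.96) = Φ(−0.553) = **29%**.
- Detectable Glut reduction: 2.6% × √4 = **5.2%**.
- Women needed for 80% power: 4 × 87.2 ≈ **350**.

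If sequence were left out, the ratio at 44:44 would be 3.46 to 3.95 for r from 0.3 to 0.9, with power of 33% down to 29%.

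**5. One baseline used as the pre value in both trials.** The baseline cancels, so the estimate is the end-of-trial difference, with true variance 2 units. The model treats the two copies as separate observations. With four rows per woman (b, b, A, B), the expected within-woman sum of squares is 4w − 6w/4 = 2.5w, where w = s²(1 − r). The residual variance is therefore about 2.5w/3 = 0.83w, and the model's variance is 4 × 0.83 = 3.33 units instead of 2.

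With the SD of the difference set to 1, w = 0.5. The model SE is √(3.33 × 0.5/88) = 0.138, and the true SE is √(2 × 0.5/88) = 0.107. Power is about Φ((0.3 − 1.96 × 0.138)/0.107) = Φ(0.28) = **61%**. Simulations of 150 and 300 trials at r = 0.5 gave 63% and 68%, with a mean model SE of 0.137.

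**6. Three-level condition model (baseline, LDX, placebo) with period and sequence.** Weights on baseline, end A and end B are 0, ½, −½, reversed in the other sequence. Variance is 2 units, and power is the stated 80%.

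**The case against.** The best defence is that the plan already points to the efficient analysis. The opening of 4.1 covers Glut by name, lists baseline, LDX and placebo as the conditions, and puts condition and sequence in a mixed model. That is almost the model in step 6. Section 4.2 sizes on within-woman change under LDX versus placebo, and with one shared baseline this is the end-of-trial difference. Aim 2 says similar models, not identical ones, and nothing assigns the baseline to Trial A.

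Much of this stands. A reader might infer that the plan commits Glut to a parallel-group test with 29% power. The documents do not support that: 29% follows from one possible coding. What remains is that the three-level list appears in a sentence about summaries, that the only treatment test spelled out is Aim 1's interaction, and that Aim 2 refers back to it. Neither literal way of fitting that test delivers the power in 4.2.

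Two further inferences also go too far. The primary outcome in 1.2, total BADDs, is not affected. The loss for cognitive performance cannot be quantified. In-office women lack a Trial B cognitive baseline, but remote women have one, and the documents do not give the split. The effect there is smaller and of unknown size.

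**Conclusion.** This is a gap in specification with a real efficiency cost, and it should be fixed. For Glut, Aim 2 carries over a test that the three-scan schedule does not support as written. Coding the baseline to Trial A quadruples the variance and gives about 29% power, or a detectable reduction of 5.2%. Re-using the baseline gives roughly 60 to 70% power. The end-of-trial contrast gives the stated 80% and 2.6% from the same scans.

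These figures rest on equal allocation, equal correlation between scans, Glut data on all 88 women, and 0.3 SD being the SD of the end-of-trial difference. Section 4.2 does not say which SD it means. If it were the SD of a difference between two changes, each with its own baseline (4 variance units), the ratio for the Trial A coding would be 8/4 = 2 and power Φ(0.3√44 − 1.96) = 51%, still below 80%. Women taking the non-imaging option give no Glut data. Their number is not stated, and power would be lower if fewer than 88 women are scanned.

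A separate minor point concerns the fMRI text of 4.1. The first-level contrast there is between emotional and neutral conditions, but no task with emotional stimuli is described, and the BOLD outcome in Aim 3 and 4.2 is the 3-back. The sentence may belong to the event-related experiments mentioned just before it, but the plan does not say so.

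**What to change.** - **Aim 2:** for Glut and cognitive performance, replace the interaction with the end-of-trial LDX versus placebo contrast. Take it from a mixed model with condition (baseline, LDX, placebo), period (Trial A, Trial B) and sequence as fixed effects and woman as a random effect.
- **Section 4.2:** state that the 0.3 SD and the 2.6% Glut figure refer to this contrast. Restate them if the pilot SD was on another scale.
- **fMRI text in 4.1:** reconcile the emotional versus neutral contrast with the 3-back outcome.

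The cost is one sentence in Aim 2, one in 4.2 and one wording check. No scan, visit or participant is added.

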Our group has explored the use of other pharmacologic strategies to target executive systems with the goal of improving symptoms of executive function difficulties. We have conducted two RCTs with medication marketed for the treatment of attention deficit hyperactivity disorder (ADHD), one with the non-psycho stimulant atomoxetine (ATX, Straterra®) and two with the pro-drug and psycho stimulant lisdexamfetamine (LDX, Vyvanse®) in the treatment of executive function difficulties in perimenopausal and menopausal women. Women who participated in the ATX study reported a significant improvement in concentration/attention and working memory domains of the Brown Attention Deficit Disorder Scale (BADDs) ([name] et al., 2011). Participants in both LDX studies were also invited to undergo the brain-imaging paradigm that is described for the current study.

[figure not shown]
Figure 1 shows the main outcome of the published results, specifically that LDX was more effective than placebo at decreasing scores in 4 of the 5 BADDs subscales ([name] et al., 2015). Findings from the imaging sub-study indicated that baseline glutamate (Glut) levels were correlated with baseline severity of total BADDs scores, meaning that individuals presenting at baseline with higher severity of executive function difficulties also had higher Glut levels within the left dorsolateral prefrontal cortex (DLPFC) at baseline. Additionally, the decline in BADDs subscale 1 (Organization and Activation) scores during LDX vs. placebo treatment was negatively associated with increase in left DLPFC blood oxygen dependent (BOLD) signal during a working memory task (N-Back). That is, the increase in left DLPFC BOLD signal to active drug compared to placebo was greater in people who had greater improvement in BADDs score on LDX vs. placebo. These findings provide important evidence of co-occurring behavioral and brain changes with LDX treatment. Applying this paradigm in a larger sample of women from whom we will also acquire neurocognitive data to assess objective changes in function will provide important information regarding the mechanism of therapeutic action of LDX in this unique population.

1 Study Objectives

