1.2 Primary Outcome Variable(s)

LDX effects on subjective report of executive function difficulties. Brown Attention Deficit Disorder Scale (BADDs) is a clinically administered 40-item questionnaire that assess the frequency and severity of five clusters of symptoms: 1) organization and activating for work, 2) sustaining attention, 3) sustaining alertness, 4) managing affective interference, and 5) using working memory and accessing recall. The total BADDs score will serve as the primary outcome variable, while sub-scale scores will be examined to more fully determine the impact of LDX treatment on various domains of executive function and to determine whether any sub-categories of executive difficulty are more responsive to LDX treatment in this particular population.

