2.1 General Design

To further our understanding of the mechanism of LDX treatment in women with executive function complaints after risk-reducing bilateral salpingo-oophorectomy (RRSO), participants will undergo multi-modal imaging (fMRI and 1H-MTS at 7 Tesla) pre- and post- a 6-week course of LDX (20-60mg/d) or placebo followed by an approximate 2-week washout before crossing over to the other condition. This study utilizes a double-blind, placebo-controlled, cross-over design. We will recruit 100 women who are between the ages of 35 and 58 years old. Subjects will be recruited from flyers posted around campus, paid advertisements, referrals from collaborators at FORCE (Facing Our Risk of Cancer Empowered), the Basser Center, and other medical settings where women who have undergone RRSO may seek treatment. Study subjects will be screened by a member of the research staff who can gauge whether the individuals are likely to meet study criteria. Potential participants who appear to meet criteria and express an interest in the study will have the option of completing the screening visit remotely or completing the visit in-office. Participants will also have the option to complete a remote version of the study.

In-Office Screening: Participants who report for an in-office screening will be presented with the full, written ICF where they will have the chance to review and sign it with the study CRC. After giving full, written informed consent, subjects will undergo screening for past and current psychiatric disorders with the Mini International Neuropsychiatric Interview (M.I.N.I) and complete several behavioral ratings and questionnaires concerning personal history. A urine sample will be collected from participants to do a urine drug screen. Subjects will then undergo a brief medical evaluation and electrocardiogram (EKG) conducted by the study PI ([name], M.D.) or key study personnel. Vital signs including blood pressure and pulse will be recorded. Women with a consistent systolic blood pressure of >145mm Hg or diastolic blood pressure >90 mm Hg after three readings at screening will not be enrolled and referred to their primary care doctors for further evaluation. Routine laboratory studies will include TSH, FSH and estrogen assays. If potential subjects have had these tests performed within the previous 6 months and can present their results, they will forgo additional blood work except that for genetics studies (4 mL)

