Remote Baseline (Visit 2): Upon completion of the screening process, subjects will be scheduled for the baseline visit which will require approximately two hours. Medication will be mailed directly to the patient's home through appropriate and approved direct-to-patient services. Subjects will be prescribed study drug for the entirety of Trial A (either placebo or LDX) and instructed to begin taking the medication as directed by the study provider. If the participant needs additional study drug in order to complete the trial an additional script will be submitted to IDS for dispensation. The subject will be sent a scale (if needed) and blood pressure cuff for future remote vital sign collections. On the day of the remote baseline visit, subjects will meet remotely with a member of the study team to complete behavioral assessments regarding their mood and emotions and complete cognitive testing.

Week 2 Phone Check-In: At the end of week 2 of medication use, the CRC will check in with the participant by phone to assess for side effects. Subjects who are having more than mild side effects will be instructed to reduce their dose back to one pill per day.

Week 3 Mid-Trial Check-In: Halfway through Trial A, during their third week, subjects will be scheduled for a remote follow-up visit where they will be monitored by the CRC for potential side effects of the medication and medication compliance. If no or mild side effects are reported, subjects will be instructed to increase the study drug to three pills per day. Subjects who are having more than mild side effects will be instructed to reduce their dose back to one pill per day. The study CRC can exercise her discretion regarding medical personnel involvement at this check-in. Subjects will be instructed to complete various mood and symptoms ratings during the visit. In total, the visit will require approximately 60 minutes and will include measures of blood pressure, pulse, and weight.

Week 4 Phone Check-In: During week 4, the CRC will check in with the participant by phone to assess for side effects. Subjects who are having more than mild side effects will be instructed to reduce their dose back to 2 pills per day for the remainder of the trial.

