2.3 Medical Administration

Subjects will be prescribed lisdexamfetamine (LDX) 20mg capsules or a look-alike placebo (microcellulose) by the study PI ([name], M.D.) or her designee. Subjects will be instructed to take one pill (LDX = 20 mg) each morning for 7 days and then will be asked to increase to two pills (LDX = 40 mg) each morning for 14 days. If the study drug is well tolerated by the end of week 3 (as per medication monitoring by the CRC), participants will be asked to increase to three pills (LDX = 60 mg) each morning until the completion of the trial. Participants will be instructed to contact the study team if they experience any side effects and may decrease their medication as instructed. At the end of week 6, which is the end of the trial, participants will be evaluated and instructed to stop their study drug. After an approximate 2-week washout, participants will be crossed over to the other condition and the procedure will repeat. See table below for dosing instructions when the substance is well tolerated.

Week	1	2	3	4	5	6
Dosage	20mg	40mg	40mg	60mg	60mg	60mg

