2.6 Study Duration

We anticipate completion of recruitment within 5 years of study inception. Each subject will spend approximately 4-5 months completing all study related procedures.

3. Subject Selection and Withdrawal

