3.1 Target Population

We will recruit 100 women, aged 35 to 58 years old, who have undergone a RRSO within the previous 15 years and are currently reporting impairment in some aspect of their daily function. We anticipate a drop-out rate of 10%. Given that the composition of the proposed study population will reflect the Greater Philadelphia referral base, we will make attempts to enhance the recruitment of minorities, but we are limited by the racial and ethnic make-up of women who typically seek oophorectomy for prevention of breast and ovarian cancer.

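### Treatment codes are opened woman by woman while later women are still being enrolled and assessed, which may weaken the blind for those later women

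*Combined protocol and SAP*

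**What the plan says.** Section 2.1 describes the trial in these words: "This study utilizes a double-blind, placebo-controlled, cross-over design". The same section, under both the End of Trial Scan and the remote end-of-trial text, has the investigator and research staff "unblind themselves to the drug treatment that was administered in each trial upon each participant's completion or discharge from the study". This is a routine step for every participant, not an emergency provision, and no reason is given for its timing.

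Other relevant text:

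- Section 1.2: the primary outcome is total BADDs score, from a "clinically administered 40-item questionnaire". The documents do not say who administers it.
- Section 2.1, Week 3 Mid-Trial Check-In: for women on study drug, "they will be monitored by the CRC for potential side effects of the medication and medication compliance". Section 2.3 makes the step to three capsules depend on tolerability, "as per medication monitoring by the CRC".
- Section 2.1, remote visits: a study-team member meets the woman for behavioural assessment and cognitive testing.
- Section 2.1, screening: the investigator has the final say on enrolment.
- Section 5.4: research staff meet weekly, and adverse events and collected data are on the agenda.
- Section 2.6: "We anticipate completion of recruitment within 5 years of study inception". Each woman is in the study for about 4-5 months.
- Section 3.1: 100 women, with 10% expected to drop out.

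**The concern.** Opening one woman's code does not directly reveal another's. The risk to later women comes by two routes.

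1. **Learned cues.** In a two-period cross-over, one opened code labels both of a woman's periods. Staff can then match her side effects, vital signs and scores to drug or placebo, and take that confirmed knowledge to the next woman.
2. **Deduced orders.** If allocation uses small fixed blocks known to staff, earlier codes could give away some later orders. The allocation method is not stated, so this route is conditional.

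The people named in the rule are not walled off from later participants. The coordinator (taken here to be research staff; section 6.1 lists coordinators among study personnel) monitors side effects and tolerability. The investigator decides on enrolment. Study-team members run the remote assessments. What is at stake is the credibility of a positive result on a subjective scale in a trial presented as double-blind. The concern is greatest for measures that staff can influence, chiefly the BADDs. Glutamate, BOLD signal and cognitive-task performance depend less on a rater's judgement.

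**Working it through.** The plan gives no figure on blinding to reproduce. Its sample size is not in dispute: with two-sided 5% alpha (sidedness assumed) and 80% power, n = ((1.960 + 0.842)/0.3)² = 87.2, rounded up to the stated 88. That calculation supplies the relevant scale, since the trial aims to detect a within-subject difference of only 0.3 SD.

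The size of any bias cannot be derived, because the documents do not show how far a rater can move BADDs answers. What can be counted is how many women the rule touches.

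**Inputs.** N = 100 (sections 2.1 and 3.1); recruitment period Y up to 5 years and time on study D = 4 to 5 months (section 2.6); drop-out 10% (section 3.1). **Assumptions.** Even accrual, and the same D for every woman. Because section 2.6 gives 5 years as an upper limit, 3 and 2 years are shown as well.

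**Formulas.** Spacing between women is s = 12Y/100 months, and woman i enrols at i × s, for i = 0 to 99. The first code opens at D.

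- Women enrolling after the first code opens: 99 − floor(D/s).
- Other women on study when a mid-trial code opens: floor(D/s).

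Example, 5 years and D = 4: s = 0.60; 4/0.60 = 6.67, floor 6; 99 − 6 = 93.

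| Recruitment | s (months) | Enrol after first code (D = 4 / 4.5 / 5) | Others on study at a mid-trial opening (D = 4 / 4.5 / 5) |
|---|---|---|---|
| 5 years | 0.60 | 93 / 92 / 91 | 6 / 7 / 8 |
| 3 years | 0.36 | 88 / 87 / 86 | 11 / 12 / 13 |
| 2 years | 0.24 | 83 / 81 / 79 | 16 / 18 / 20 |

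Counting assessment rather than enrolment, every woman but the first, 99 of 100, has her last assessment after the first code could be opened. Drop-out adds 10% × 100 = 10 codes opened at discharge, possibly before 4 months.

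**Block route, conditional only.** If a fixed block of size b were used and known, and all earlier codes in the block were open, the chance that a woman's order is fully determined by her last assessment is 1/(b/2 + 1): 50% for b = 2, 33% for b = 4, 25% for b = 6. Under simple randomisation or undisclosed variable blocks it is about 0%.

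**The case against.** The strongest reply is that the harm rests on a chain the documents do not complete. The same staff would have to rate later women, the confirmed codes would have to add to what staff already suspect, and raters would have to be able to shift answers. The first and third links are not documented for the BADDs. On the second, side effects listed in section 5.1 would give staff cues in any case, and the Background reports earlier trials by the group, "two with the pro-drug and psycho stimulant lisdexamfetamine". The woman is also the informant on a scale of her own complaints, and the rule does not say that participants are told their order. One opened code teaches little, so counting women after the first code overstates meaningful exposure. The block route is conjecture without a stated allocation method.

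Much of this stands as a limit on size. A completed woman's own ratings are untouched, and functional unblinding and prior experience would remain whatever is done with the codes. Holding codes removes only what confirmed codes add. The block route should carry no weight in grading the point.

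It does not defeat the point. Staff contact with later women is documented in several places, nothing separates unblinded staff from assessors, and no passage gives a benefit from opening codes early. Section 5.4 makes the investigator the primary safety monitor, but no text says that opened codes serve that purpose.

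**Conclusion.** The concern holds. As written, the rule exposes later women's staff contacts and ratings to an avoidable loss of blinding. Under even accrual over 5 years it reaches 91-93 of 100 women before they enrol; over 2 years it still reaches 79-83. These are counts of women exposed, not estimates of how much their ratings would move, and they depend on even accrual and a common 4-5 months on study. Sample size and power are unaffected. Because the bias cannot be sized and may be small, this is a recommended change rather than a fatal flaw, held with medium confidence.

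**What to change.** Replace the sentence in both places in section 2.1 with wording such as:

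> Treatment codes are held outside the study team. The investigator, coordinators and raters stay blinded until the last participant's data are locked. Emergency unblinding is per participant and documented.

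The holder could be the Investigational Drug Service, which already dispenses the study drug (section 8.1); this needs confirming. If someone must see codes earlier, a narrower alternative is to restrict that to a person with no role in enrolment, titration or rating. Stating the allocation method would settle the block question.

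**Cost.** Protocol wording in two places and confirmation of the code holder; no change to visits, sample size or analysis. The real downside is delay: staff, and participants if they are told at all, learn the order later. From a woman's own completion to the last participant's last visit, the wait over 5 years is 99 × 0.60 = 59.4 months for the first completer and 49.5 × 0.60 = 29.7 months for the median woman. Over 3 years it is 99 × 0.36 = 35.6 and 49.5 × 0.36 = 17.8 months. Time to data lock is added in each case. If the sponsor does intend opened codes to support safety review, the protocol should say so and name someone outside the assessing team to do it.
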